6.2. Exclusion Criteria

- 1. Active herpes zoster disease in past 6 months preceding the first dose of study vaccine
- 2. If female, planning to get pregnant, currently pregnant (evidence from positive serum or urine pregnancy test), or breastfeeding.
- 3. Used any investigational or non-registered product other than the study vaccine within 30 days preceding the first dose of study vaccine or planned use during the study period.
- 4. Vaccinated within the 12 months preceding the first dose of study vaccine or planned to be vaccinated during the study with a (non-study) vaccine against herpes zoster or varicella zoster virus.
- 5. History of any reaction or hypersensitivity likely to be exacerbated by any vaccine component.
- 6. Received or planned to receive a live vaccine in the period starting 30 days before the first dose of study vaccine and ending 30 days after the last dose

of study vaccine or had received or planned to receive a non-replicating vaccine within 8 days before or within 14 days after either dose of study vaccine.

- 7. Acute disease and/or fever at the time of enrolment; Fever is defined as temperature ≥ 37.5°C (99.5°F) on oral, axillary or tympanic setting. The preferred route for recording temperature in this study will be oral. Subjects with a minor illness (such as mild diarrhoea, mild upper respiratory infection) without fever may, be enrolled at the discretion of the investigator.
- Chronic administration (defined as more than 15 consecutive days) of immunosuppressants or other immune-modifying drugs within six months prior to the first vaccine dose. For corticosteroids, this will mean prednisone < 20 mg/day, or equivalent, is allowed. Inhaled and topical steroids are allowed.

Drugs include: Chemotherapeutic drugs, Immunomodulators and systemic immunosuppressive treatments, Oral glucocorticoids >20 mg/day, Cyclosporine, Methotrexate, Interleukins and/or cytokines, Immunotherapies (including TNF blockers).

- 9. Any other clinical condition that, in the opinion of the investigator, might pose additional risk to the subject due to participation in the study.
- 10. History of potential immune-mediated disease (pIMD). Note: If the subject has any condition on the list of pIMDs specified in the protocol, they must be excluded unless the aetiology is clearly documented to be non-immune mediated.

6.3. Selection of Participants

Participants will be recruited from HIV clinical centres which jointly provide medical care for over 10,000 PLWH: and combined have one of the largest European cohort of individuals with perinatally acquired HIV infection.

We will recruit up to 70 HIV positive adults with the aim for n=31 \geq 50 years old and n=31 adults with perinatally acquired HIV over the age of 18 years who have completed the study.

6.4. Co-enrolment guidance

Participants should not be participating in any other vaccine study within 30 days prior to enrolment, nor should they co-enrol into any other interventional studies that are deemed to impact on the primary or secondary outcomes for the duration of their participation in the SAGE trial. If they do, they will be omitted from the primary immune analysis.

6.5. Participant Identification and Consent

Potential participants will be identified and approached by their direct healthcare team within their regular outpatient clinic. If interested and agree, the potential participant will be referred to the to the research team for further information and provided with an information sheet. Once the potential participant has had an opportunity to review the information, if they are still interested and consent, they will be booked into a screening visit where written informed consent will be obtained by a trial investigator.

The Principal Investigator (PI) retains overall responsibility for the conduct of research at their site, this includes the taking of informed consent of participants at their site. They must ensure that a delegated medic who is responsible to participate in the informed consent process is duly authorised, trained and competent to participate according to the ethically approved protocol, principles of Good Clinical Practice (GCP) and Declaration of Helsinki.

Written informed consent must be obtained prior to the participant undergoing procedures that are specifically for the purposes of the trial and are out-with standard routine care at the participating site.

6.6. Randomisation Procedure / Code Break

There is no Randomisation.

6.7. Withdrawal of Participants

Participants have the right to withdraw from the study at any time for any reason. The investigator also has the right to withdraw participants from the study drug in the event of inter-current illness, AEs, SAEs, SUSARs, protocol violations, cure, administrative reasons or other reasons. It is understood by all concerned that an excessive rate of withdrawals can render the study un-interpretable; therefore, unnecessary withdrawal of participants should be avoided. Should a participant decide to withdraw from the study, all efforts will be made to report the reason for withdrawal as thoroughly as possible. Should a participant withdraw from study vaccination only, efforts will be made to continue to obtain follow-up data, with the permission of the participant. Any samples and/or data already obtained prior to withdrawal will be used in the analysis.

Participants who wish to withdraw from study vaccination will be asked to confirm whether they are still willing to attend for the subsequent study visits.

To ensure trial endpoints are met, 62 participants will need to have received both injections. The sample size calculations therefore allow for up to 70 participants to be recruited to ensure this occurs. Participants who withdraw prior to their second injection will therefore be replaced up to an including when 62 participants have received 2 vaccinations.

In all cases the date and reasons for withdrawal or withholding the dose of medication will be clearly stated on the participant's CRF. If the reason for removal of a participant from the trial is an adverse event or an abnormal laboratory test result, the principal specific event or test will be recorded on the CRF.

6.8. Expected Duration of Trial

Participants will be on study for approximately 48 weeks, though may be extended due to generous visit window periods. The end of trial will be defined as data lock.

7. Trial Procedures

Table 1 summarises the list of study procedures to be followed during the study visits and at the study conclusion contact. Table 2 summarises study procedures to be performed for the follow-up of each suspected HZ case.

7.1. By Visit

This prospective multicentre study will recruit up to 70 individuals attending HIV services. Individuals will attend for visits at screening, baseline (vaccination), week 4, week 8 (vaccination), week 12, week 24 and week 48. Research and safety bloods will be taken at each visit. Study participants will receive 2 intramuscular doses of HZ/su 2 months apart. Vaccine reactogenicity review will occur 15 minutes post vaccination.

Any individual who develops shingles after vaccination will have swabs taken for viral diagnosis and viral sequencing.

The trial assessment schedule consists of a screening visit (visit 1) followed by an enrolment visit which defines week 0 (visit 2). If preferred by the participant, both visits can occur on the same day.

The first injection will take place at week 0 (visit 2) and the second injection visit is at week 8 (visit 4). Follow-up visits to ask about all adverse events and take blood are at weeks 12, 24 and 48 (visits 5,6,7). Additional visits may be undertaken if indicated, for example to investigate or follow-up an adverse event or abnormal laboratory result or if a participant develops symptoms suggestive of shingles.

The required volumes per visit together with sample collection and processing guidelines are described in detail in the laboratory manual. Required volumes of samples analysed by local laboratories (i.e. safety and HIV parameters) might vary according to local standard procedures. The visit windows are defined in the in Table 1.

Biological samples to be collected: -

Blood samples will be collected from all subjects at every visit to evaluate safety and/or immunogenicity. Should the participant experience a suspected HZ episode, swabs from the lesion and a blood sample will be collected.

Study details: Study subjects will be provided with a subject card which contains the address and telephone number of the main contact for information about the trial. The aim of this card is to inform any physician having to deal with a subject in an emergency situation that the subject is in a clinical trial and that he/she can contact the trial investigator for more relevant information. Subjects must be instructed to keep these cards in their possession at all times.

Study Assessments and Procedures

Refer to the Table 1, for the visit schedule. Note that unscheduled visits may be required. Immediate safety concerns should be addressed by the PI as soon as he or she becomes aware of the concern to determine if the participant should continue or discontinue study vaccination. The PI will inform the Sponsor immediately upon occurrence or awareness. Adherence to the study design requirements, including those specified in the visit schedule, is essential and required for study conduct. All participants will be enrolled and followed up for 48 weeks. The vaccination phase will last 8 approximately weeks.

Procedures prior to study participation

Potential participants will be identified through HIV clinics. Eligible individuals will be informed about the trial and given a patient information sheet at least one day prior to consent is taken which explains the aims, methods, and potential benefits and hazards of the trial.

Screening visit

The study staff conducting the Screening visit will:

- Introduce themselves and their role to the participant and confirm the identity of the participant.
- Confirm that the means of contact is adequate to conduct the contact/visit

• Participants will be provided with the study information, including the participant information sheet (PIS) to read. They will discuss the study with a member of the research team in person or remotely. Consent will be obtained by an investigator.

After informed consent has been collected, a unique trial identifier will be assigned by the study staff. The screening visit will conduct:

- Eligibility assessment (as per inclusion/exclusion criteria)
- Demographics recording
- Medical History
- Vital signs
- Temperature

- Full physical exam
- Urine pregnancy test (women of childbearing potential only)
- Concomitant medications review
- Adverse Events Review

Procedures prior to the first vaccination at enrolment visit

Screening and enrolment can occur on the same day. If not, the enrolment visit should take place within 8 weeks following the screening visit. If more than 8 weeks have elapsed study repeat the screening assessments.

Study staff will review information related to eligibility collected at screening and determine whether there are any clinically relevant abnormalities that require further investigation prior to enrolment.

Baseline, Week 0 (+8 weeks)

The baseline visit will conduct:

- Eligibility Assessment (as per inclusion/exclusion criteria)
- Vital signs
- Temperature
- Directed physical exam
- Concomitant Medication review
- Vaccination
- Vaccine reactogenicity, unsolicited adverse event & IMD review
- Participant survey: beliefs about shingles and shingles vaccines
- Urine pregnancy test (women of childbearing potential only)
- Venepuncture for:
 - CD4 (CD4:CD8)
 - o HIV Viral Load
 - o Hepatitis BsAg
 - Safety blood sample (FBC, U&E, ALT)
 - Immunology blood sample
 - Serology blood sample

Note: Pregnancy test will be performed even if the subject is menstruating at the time of the study visit. The study vaccine can only be may only be administered if the pregnancy test is negative.

Check contraindications to vaccination: Contraindications to vaccination are to be checked at the beginning of each vaccination visit. Furthermore, any subject with a clinically diagnosed HZ episode between Visit 1 and Visit 2 should receive the second vaccination 3 months after the day of onset of shingles.

Vaccination Visits: 2 (Baseline) & 4

Prior to injection, study staff will conduct an inspection of the site where injections will be administered in each arm as part of the directed physical examination. The axillary, oral or tympanic body temperature of all subjects will be measured prior to any study vaccine administration. The preferred route for recording temperature in this study will be oral. All vaccines may be administered to persons with low-grade fevers, i.e., oral, tympanic on oral setting, or axillary temperature < 37.5°C. If a subject has an axillary/oral/tympanic on oral setting temperature \geq 37.5°C, it will constitute a contraindication to administration of vaccine.

Study staff should administer the injection into the deltoid muscle of the designated upper arm and record this in the appropriate CRF including the time of injection.

The Shingrix vaccine dose, after reconstitution, is 0.5 ml in volume and should be injected into the deltoid muscle of the non-dominant arm. Following injection participants should remain in clinic, in order to assess vaccine reactogenicity and solicited adverse events at 15 minutes following injection.

If the Investigator or delegate determines that the health on the day of vaccination temporarily precludes vaccination, the visit will be rescheduled within the window period for this visit.

The vaccinees will be observed for 15 minutes, with appropriate medical treatment readily available in case of anaphylaxis, following the administration of vaccine.

All injections will be administered by delegated and suitably trained site staff.

Visit 3, week 4 (+/- 4 weeks)

The following will be conducted:

- Vital signs
- Directed Physical Exam
- Concomitant Medication Review
- Solicited and Unsolicited Adverse Event & IMD Review
- Venepuncture for:
 - Immunology blood sample
 - Serology blood sample

Visit 4, week 8 (-4/+7 weeks)

- Vital signs
- Temperature
- Directed Physical Exam
- Concomitant Medication Review
- Unsolicited Adverse Event & IMD Review
- Urine pregnancy test (women of childbearing potential only)

- Vaccination
- Venepuncture for:
 - Immunology blood sample
 - Serology blood sample

Visit 5, week 12 (+/- 4 weeks)

- Directed Physical Exam
- Concomitant Medication Review
- Solicited and Unsolicited Adverse Event & IMD Review
- Venepuncture for:
 - Immunology blood sample
 - Serology blood sample

Visit 6 week 24 (+/- 4 weeks)

- Directed Physical Exam
- Concomitant Medication Review
- Unsolicited Adverse Event & IMD Review
- Venepuncture for:
 - o HIV Viral load
 - o Safety blood sample
 - Immunology blood sample
 - Serology blood sample

Visit 7, week 48 (+/- 4 weeks)

- Directed Physical Exam
- Concomitant Medication Review
- Unsolicited Adverse Event & IMD Review
- Venepuncture for:
 - CD4 (CD4:CD8)
 - HIV Viral load
 - Safety blood sample
 - Immunology blood sample
 - Serology blood sample

Participant transfers

It is extremely unlikely that a participant will move from one trial centre to another, but not impossible. In the event that a participant does transfer, a copy of the participant's CRF should be provided to the new site and the participant will need to sign a new consent form. Once this has been done, the new site will take over responsibility for the participant; until this has been done, responsibility for the participant lies with the original site.

Recording of non-serious AEs and SAEs

• Refer to Section 8 for procedures for the Investigator to record AEs and SAEs.

• The subjects will be instructed to contact the investigator immediately should the subject manifest any signs or symptoms they perceive as serious.

Evaluation and confirmation of suspected and confirmed HZ cases

A suspected case of HZ is defined as new unilateral rash accompanied by pain (broadly defined to include allodynia, pruritus or other sensations) and no alternative diagnosis. Subjects clinically diagnosed as having a suspected case of HZ by the investigator will be referred to as a case of 'clinically diagnosed suspected HZ' and followed up.

Determination of confirmed cases of HZ for efficacy analyses is provided by routine clinical PCR. The HZ onset date is the earlier of the following two events: 1) the HZ rash start date; or 2) the date on which pain at the site of a subsequent HZ rash is first noted. The HZ onset date will be confirmed by the investigator and recorded in the eCRF.

Rash lesion samples (two replicate samples on the same day) will be collected from subjects clinically diagnosed as having a suspected case of HZ. If more than one site is involved then swabs needed to be taken from each site – including if systemic symptoms are present, CSF or other bodily fluids).

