5.5.1. Dosage Preparation and administration of study vaccine

The powder and suspension should be inspected visually for any foreign particulate matter and/or variation of appearance. If either is observed, do not reconstitute the vaccine.

How to prepare Shingrix:

Shingrix must be reconstituted prior to administration.

- 1. Withdraw the entire contents of the vial containing the suspension into the syringe.
- 2. Add the entire contents of the syringe into the vial containing the powder.
- 3. Shake gently until the powder is completely dissolved.

The reconstituted vaccine is an opalescent, colourless to pale brownish liquid.

The reconstituted vaccine should be inspected visually for any foreign particulate matter and/or variation of appearance. If either is observed, do not administer the vaccine.

After reconstitution, the vaccine should be used promptly; if this is not possible, the vaccine should be stored in a refrigerator $(2^{\circ}C - 8^{\circ}C)$. If not used within 6 hours it should be discarded.

Before administration:

1. Withdraw the entire contents of the vial containing the reconstituted vaccine into the syringe.

2. Change the needle so that you are using a new needle to administer the vaccine.

Any solution in excess of 0.5mL should be expelled. After confirming that the needle is not in a blood vessel, the reconstituted vaccine should be administered by IM injection, preferably into the deltoid muscle of the non-dominant upper arm, using a standard aseptic technique. The injection site should be on the same arm for all injections for an individual subject. In rare situations when there is no other alternative, the second injection may be given on the different arm.

Contraindications to subsequent vaccination

The following events constitute absolute contraindications to further administration of the vaccine. If any of these events occur during the study, the subject must not receive additional doses of vaccine but may continue other study procedures at the discretion of the investigator.

• Anaphylaxis following the administration of vaccine(s);

• Acute disease and/or fever at the time of vaccination. – Fever is defined as temperature \geq 37.5°C (99.5°F) on oral, axillary or tympanic setting. The preferred route for recording temperature in this study will be oral. Subjects with a minor illness (such as mild diarrhoea, mild upper respiratory infection) without fever can be administered all vaccines.

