9.3. Protocol vaccine discontinuation

In consenting to the trial, participants are consenting to receive vaccines, to attend the visits for trial follow-up and to provide information that supports data collection.

An individual participant may stop injections early or be stopped early for any of the following reasons:

- Pregnancy in the participant
- > Unacceptable toxicity that precludes further injections
- Intercurrent illness that prevents further injections including emergent conditions that meet the exclusion criteria
- > Withdrawal of consent for injections by the participant

A decision to discontinue further injections should be taken in consultation with the local PI.

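### Two second-dose rules are wrong as written: the 3-month shingles delay names the screening-to-dose-1 interval, and section 5.5.1 makes fever on the day a permanent bar (minor)

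*Protocol*

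**What the plan says.** **Shingles before dose 2.** Protocol section 7.1, under the check of contraindications, states that "any subject with a clinically diagnosed HZ episode between Visit 1 and Visit 2 should receive the second vaccination 3 months after the day" (counted from shingles onset). The same section fixes the visit numbers: "The first injection will take place at week 0 (visit 2) and the second injection visit is at week 8 (visit 4"). Visit 1 is screening. It may fall on the same day as Visit 2; otherwise "the enrolment visit should take place within 8 weeks following the screening visit", and screening is repeated if the gap is longer. Exclusion criterion 1 in section 6.2 is "Active herpes zoster disease in past 6 months preceding the first dose of study vaccine", and 7.1 repeats the eligibility assessment at baseline.

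Two general provisions also touch the case. Section 7.1 has the principal investigator address immediate safety concerns "to determine if the participant should continue or discontinue study vaccination". Section 9.3 lets a participant stop injections for "Intercurrent illness that prevents further injections including emergent conditions that meet the exclusion criteria".

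**Fever or acute disease on the day.** Section 5.5.1 gives a list of absolute contraindications to further doses and adds: "If any of these events occur during the study, the subject must not receive additional doses of vaccine". The list has two items: anaphylaxis and "Acute disease and/or fever at the time of vaccination", with fever set at 37.5°C or more. Section 7.1 treats the same temperature as a contraindication to giving the vaccine, without calling it absolute. It then has the visit rescheduled within its window when the person's health that day rules out vaccination only temporarily.

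**The concern.** Both are operative dosing rules that sites will follow, and read literally both give a result that nobody can have wanted.

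The shingles rule governs the second dose but is triggered by an episode before the first. If it is followed as printed, someone whose shingles comes and goes between the doses gets dose 2 on the usual schedule, while a site that guesses the intent would wait 3 months. Under 5.5.1, a passing temperature of 37.5°C at Visit 4 ends vaccination for good, while a site working from 7.1 would rebook. Sites could therefore treat the same event differently in a trial that needs 62 people to have had both injections (section 6.7) and whose primary timepoint is defined relative to dose 2 (section 4.2).

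**Working it through.** The protocol states no figure for this point, so there is nothing to reproduce. The check sets the rules side by side, works out the timing, and estimates how often the shingles rule would be needed.

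**Conversions.** 3 months = 3 × 365.25 / 12 / 7 = 13.04 weeks. In the same way, 2 months = 8.7, 4 months = 17.4 and 6 months = 26.1 weeks.

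**1. The rule as printed.** Visits 1 and 2 are 0 to 8 weeks apart, so an episode between them starts at most 8 weeks before dose 1. That lies wholly inside the 26.1 weeks barred by criterion 1. With same-day screening and baseline the interval is empty. The rule therefore applies to no eligible participant. Its arithmetic confirms the mismatch: onset at weeks −8 to 0 puts dose 2 at −8 + 13 = week 5 to 0 + 13 = week 13, so a rule meant to delay could bring dose 2 forward from week 8.

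**2. The rule with Visits 2 to 4.** Dose 2 = onset + 13 weeks. Section 7.1 says that Table 1 defines the visit windows, so Table 1 is used here: Visit 4 at 8 ± 3 weeks, closing at week 11.

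| Onset (week) | Dose 2 (week) | Sample 4 weeks later (week) |
|---|---|---|
| 0 | 13 | 17 |
| 8 | 21 | 25 |
| 11 | 24 | 28 |

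- Dose 2 always falls after the Visit 4 window (13 > 11), so the corrected rule needs an exemption from it.
- The sample always falls after the Table 1 Visit 5 window, which closes at 12 + 3 = week 15 (17 > 15). It can meet Visit 6, which runs over weeks 21 to 27.
- Dose 2 at week 24 is inside the 6-month maximum spacing (26.1 weeks) quoted from the SmPC in section 3.

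**3. Contraception.** Section 6.1 requires cover through month 4, about week 17.4 if counted from baseline. Section 5.3 requires it until 2 months after dose 2. With dose 2 at week 13 that means 13 + 8.7 = week 21.7; at week 24 it means week 32.7. The month-4 limit is too short in both cases.

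**4. Expected shingles cases between doses.** Inputs from section 3: about 5 to 10 per 1000 per year at age 50 and over, 2 to 3 per 1000 below age 40, and a 3- to 5-fold excess in people with HIV on treatment. Group size 31 each (section 6.3). Assumption: the perinatal group has the under-40 rate times the same excess. The protocol suggests earlier shingles in this group but gives no rate. No vaccine effect is allowed for.

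- Low: 31 × (0.005 + 0.002) × 3 × 8/52 = 0.10
- High: 31 × (0.010 + 0.003) × 5 × 8/52 = 0.31
- Chance of at least one case: 1 − exp(−0.10) ≈ 10% to 1 − exp(−0.31) ≈ 27%

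**5. Fever.** For 37.5°C at Visit 4, section 5.5.1 gives no further doses. Section 7.1 gives no dose that day and, if the problem is temporary, a new date within the window. Section 9.3 says only that a participant may stop, so it does not settle which applies. The protocol gives no rate of fever on the day, so no count is offered.

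**The case against.** The best defence is that the intended meaning is easy to see. The sentence speaks of the second vaccination, and criterion 1 leaves the printed interval empty, so a reader will take it as dose 1 to dose 2. A specific 3-month rule for a rare event can also be read as an exception to the general Visit 4 window. On fever, the rescheduling sentence stands in the same block of 7.1 as the temperature rule, so sites working from the visit procedures would probably rebook; that sentence does not name fever, so the conflict rests on its natural reading. All of this lowers the stakes, but a dosing rule should not depend on readers correcting it, and the literal bar in 5.5.1 stands however 7.1 is read.

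A reader might infer more than the text supports:

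- *That shingles between doses is not handled at all.* Shingles still active at Visit 4 can be treated as acute disease under 5.5.1, or as a temporary obstacle under 7.1. The uncovered case is shingles that has resolved by then.
- *That the delayed dose 2 breaches the 6-month spacing.* Under Table 1 it does not. It could only if the conflicting 7.1 window for Visit 4 (+7 weeks, to week 15) were used: 15 + 13 = week 28.
- *That the shingles rule causes primary samples to be taken before dose 2.* With Visit 4 allowed to week 15 under 7.1, a calendar week-12 sample can precede dose 2 without any shingles. That is a separate conflict between windows, and the endpoint is in any case defined as 4 weeks after dose 2.

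**Conclusion.** Both rules are wrong as written, and the point is minor. The shingles delay names an interval with no eligible participants and leaves shingles resolved before Visit 4 without an applicable delay. That Visits 2 to 4 were meant is an inference, but a strong one. Section 5.5.1 turns a passing fever or acute illness into a permanent loss of dose 2, against the natural reading of 7.1.

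The expected size is about 0.1 to 0.3 shingles cases between doses over 8 weeks, resting on the assumed perinatal rate and no vaccine effect. Fever is not quantified. Section 6.7 also allows replacement of people who withdraw before dose 2. A reader might infer bias in the primary estimate or harm to participants. Neither is shown: the expected numbers are very small, and the protocol gives no reason for the 3 months from which a safety effect could be argued.

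**What to change.** Subject to the investigators' clinical agreement:

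1. **Section 7.1, shingles rule.** Change the interval to Visit 2 to Visit 4. State that a dose 2 delayed under this rule is exempt from the Visit 4 window.
2. **Section 7.1, Visit 5.** For a delayed dose 2, take the primary sample 4 weeks after the actual dose, outside the Visit 5 window, and combine it with Visit 6 where the two coincide.
3. **Section 6.1, contraception.** Replace the month-4 limit with 2 months after the actual dose 2, in line with 5.3.
4. **Section 5.5.1.** Keep anaphylaxis as the absolute contraindication. Make acute disease or fever on the day a temporary deferral, rescheduled as in 7.1.

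The cost is a wording amendment to sections 5.5.1, 6.1 and 7.1. It adds no procedures and no participants. The only added burden is longer contraception for women of childbearing potential whose dose 2 is given late.

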For individuals living with HIV, British HIV association (BHIVA) vaccine guidelines 2015 November recommend that patients ≥60 years of age (provided the CD4 cell count is >200 cells/µL) should receive the shingles vaccine (Zostavax) vaccine [Aberg 2014], which is 10 years younger than national recommendations. There are safety and efficacy concern however, giving this live vaccine to "special populations" such as those with a low nadir CD4 [Benson 2012] or those with perinatal infection in which shingles vaccines have not been evaluated at all.

Thanks to the continuously increasing coverage of ART-based prophylaxis and treatment, in 2018, MTCT incidence was under 2%, and about 50% of children living with HIV were receiving ART [UNAIDS 2019]. Therefore, an increasing number of children start ART at a very young age and will be receiving antiretroviral drugs for all their lifetime. ART greatly improved their survival and the quality of life [Gibb 2003: Judd 2007], but on the other hand, they now face the consequences of a lifelong chronic condition, suffering from pathogenic mechanisms typical of premature aging [Deeks 2009: Brady 2010: Chiappini, 2014: Guaraldi 2017]; i.e., they show an increased risk of age-associated comorbidities, identified as non-AIDS-related diseases [Klein 2011: Brouilette, 2007: Takata 2012], compared to healthy individuals [Deeks 2012: Guaraldi, 2011: Smith 2013]. Those with perinatal infection have poor immune function for a variety of reasons: such early HIV infection impacts T-Cell memory (McCarty 2018), poor access to ART during childhood (UNAIDS 2019), partly as paediatric formulations were not readily available until 2000, and finally their adherence to ART is often variable during early and teenage years for sociological reasons [MacDonell 2016: Gray 2017: Schlatter 2016]. Such young individuals, who are at risk of Shingles, historically find it difficult to attend for regular follow up. Therefore to mimic real life, this study has included large window periods. This will not impact vaccine efficacy, which allows up to 6 months between vaccination (Santos Virology 2000: Tipples Emerg Inf Dis 2002). furthermore, if vaccinations are being given earlier than previously recommended then knowledge of the duration of protection is imperative to be able to inform on recommendations for booster vaccination.

Shingrix vaccine

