4.2. Primary endpoints

1. Total VZV specific cell mediated geometric mean titer (GMT) ratios change from baseline to week 12 (4 weeks after second vaccine dose).

2.Total VZV specific antibody geometric mean titer (GMT) ratios change from baseline to week 12 (4 weeks after second vaccine dose).

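### Both primary endpoints are set at 4 weeks after dose 2, but Visit 5 is windowed from week 0 under two conflicting sets of windows, so the sample may fall about 0 to 10 or 0 to 12 weeks after dose 2

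*Protocol*

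**What the plan says.** Section 4.2 of the protocol defines both primary endpoints, cell-mediated and antibody, as "ratios change from baseline to week 12 (4 weeks after second vaccine dose". The synopsis and Sections 8.1.1, 10.1 and 10.3 repeat that timing.

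Section 7.1 fixes the origin of the week count: screening is "followed by an enrolment visit which defines week 0 (visit 2". It then states: "The first injection will take place at week 0 (visit 2) and the second injection visit is at week 8 (visit 4". Visit 5 is week 12 on the same scale. Nowhere is Visit 5 counted from the date on which dose 2 was actually given.

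The windows appear twice:

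- Table 1 (Section 4.6) gives plus or minus 3 weeks for Visits 3 to 7.
- The visit list in Section 7.1 gives "Visit 4, week 8 (-4/+7 weeks" and "Visit 5, week 12 (+/- 4 weeks", and plus or minus 4 weeks for Visits 3, 6 and 7.

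Earlier in the same Section 7.1 stands the sentence "The visit windows are defined in the in Table 1".

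Section 3 explains the wide windows by the difficulty that young people at risk have had in attending regularly. It adds: "This will not impact vaccine efficacy, which allows up to 6 months between vaccination".

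**The concern.** There are two faults, and they compound each other.

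The first is a plain contradiction. A site reading Table 1 and a site reading the visit list will disagree on whether a week-14 second dose or a week-16 primary sample is in window, although Section 7.1 calls adherence to the visit schedule essential.

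The second is that neither set of windows delivers the endpoint as defined. The endpoint is timed from dose 2. Dose 2 and Visit 5 each move independently around a calendar week counted from dose 1. A participant can be in window at both visits and still be sampled well away from 4 weeks after dose 2. The week-12 ratio would then pool responses measured soon after dose 2 with responses measured many weeks later.

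The reason given for the wide windows does not answer this. It concerns how far apart the two doses may be, not how long after dose 2 the response is measured. The protocol also expects irregular attendance among the young participants, so use of the window edges may differ between the two groups. The groups are analysed separately, but Section 3 says the study will allow responses to be compared across age groups.

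**Working it through.** Inputs, in weeks from week 0 (the first-dose visit, Section 7.1):

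- Table 1: Visit 4 (dose 2) is 8 ± 3, so weeks 5 to 11. Visit 5 (primary sample) is 12 ± 3, so weeks 9 to 15.
- Section 7.1: Visit 4 is 8 −4/+7, so weeks 4 to 15. Visit 5 is 12 ± 4, so weeks 8 to 16.

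**The plan's own figure.** Nominal interval from dose 2 to sample = 12 − 8 = 4 weeks. This reproduces.

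**Permitted interval for a given dose-2 week d.** Latest = (close of Visit 5 window) − d. Earliest = (opening of Visit 5 window) − d, set to 0 where that is negative, because visit order is kept.

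| Windows | Dose 2 at week d | Earliest | Latest |
|---|---|---|---|
| Table 1 | 5 | 9 − 5 = 4 | 15 − 5 = 10 |
| Table 1 | 8 | 9 − 8 = 1 | 15 − 8 = 7 |
| Table 1 | 11 | 9 − 11 = −2, so 0 | 15 − 11 = 4 |
| Section 7.1 | 4 | 8 − 4 = 4 | 16 − 4 = 12 |
| Section 7.1 | 8 | 8 − 8 = 0 | 16 − 8 = 8 |
| Section 7.1 | 12 | 8 − 12 = −4, so 0 | 16 − 12 = 4 |
| Section 7.1 | 15 | 8 − 15 = −7, so 0 | 16 − 15 = 1 |

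With visit order kept, the overall range is about 0 to 10 weeks under Table 1 and about 0 to 12 weeks under Section 7.1. Even with dose 2 given exactly at week 8, the range is 1 to 7 or 0 to 8 weeks.

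**Can a 4-week sample always be taken in window?** It falls at week d + 4.

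- Table 1: d = 5 gives week 9 and d = 11 gives week 15. Both are inside 9 to 15, so it always fits, though nothing requires it.
- Section 7.1: d + 4 exceeds 16 whenever d exceeds 12. For dose 2 after week 12 and up to week 15, the 4-week sample lies outside the Visit 5 window.

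**After anchoring Visit 5 to dose 2.** Centred 4 weeks after the actual dose, a half-width of 3 gives 4 − 3 = 1 to 4 + 3 = 7 weeks. A half-width of 4 gives 0 to 8 weeks.

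**Side check on sample size.** With the Section 10.1 inputs (width 3, SD 3.4; width 0.6, SD 0.7; probability 0.90), the one-mean confidence-interval-width calculation returns 30 and 31 per group, as stated. The timing problem does not alter these numbers, but they limit how many samples the primary analysis can lose: about 35 recruited − 31 needed = 4 per group.

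**The case against.** The strongest defence is that the protocol says Table 1 governs. Under Table 1 a 4-week sample always fits, and the 10-week extreme needs the earliest dose 2 paired with the latest Visit 5. This stands as far as it goes. The 12-week limit and the case where a 4-week sample cannot be taken in window belong to Section 7.1 alone. But the conflicting windows are printed in the visit-by-visit instructions, and Table 1 still allows about 0 to 10 weeks.

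A reader might infer that the primary sample may be taken before dose 2. Read literally, the windows do not exclude it, by up to 2 weeks (Table 1) or 7 weeks (Section 7.1). That requires Visit 5 to precede Visit 4. The visit numbering and the solicited adverse event review at Visit 5, which serves the second dose, imply that this will not happen. It is a gap in the wording, not an expected event.

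A reader might also infer that week 48 has the same fault. The documents do not support that: the week-48 endpoints run from baseline to week 48 with no reference to dose 2, so a calendar window agrees with their definition.

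Finally, it can be said that handling off-time samples belongs in a statistical analysis plan, which is not at hand. That is true of the analysis, and the injection is recorded in the CRF. But such a plan cannot create a sample that was not drawn at the right time, nor decide which printed window the sites follow.

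**Conclusion.** The point holds. The protocol prints two incompatible sets of windows, and under neither is the primary sample tied to dose 2 as the endpoint definition requires. The permitted interval, against a stated 4 weeks, is about 0 to 10 weeks under Table 1 and about 0 to 12 weeks under Section 7.1. Under Section 7.1, dose 2 at week 15 leaves at most 1 week before the Visit 5 window closes.

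This rests on two assumptions: weeks are counted from the first-dose visit, as Section 7.1 says, and visits take place in their numbered order. The figures are permitted intervals, not a forecast of attendance. The documents contain no data on how the response changes with time after dose 2, so neither the direction nor the size of any bias in the geometric mean ratio can be stated. A confidence interval would not reflect a systematic shift in timing.

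**What to change.** - Reconcile Table 1 and Section 7.1 into one set of windows for Visits 3 to 7. Which dose-2 window is right is for the sponsor to decide.
- Schedule Visit 5 at 4 weeks from the actual date of dose 2, with a window that opens after dose 2. A half-width of 3 weeks meets this (1 to 7 weeks); a half-width of 4 weeks reaches back to the day of dose 2 itself.
- Add an eCRF check of the Visit 5 date against the recorded dose-2 date.
- Keep all available week-12 samples in the primary analysis, so that the 31 per group needed for the stated precision is not eroded. Add a sensitivity analysis restricted to samples inside the dose-2-anchored window.

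The cost is a change of protocol wording and later calendar dates for some Visit 5 appointments. For example, if the reconciled windows still allowed dose 2 at week 15, Visit 5 would be centred on week 15 + 4 = 19. No added visits or participants are needed.
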